10.6.4. Safety

Extent of Exposure

- Number of days of exposure to study drug will be calculated based on the formula:
Duration of Exposure in Days = Last mepolizumab dose – (First mepolizumab dose) + 29
- The extent of exposure will also be summarised as the number of study treatments administered

Adverse Events

Adverse Events of Special Interest

Section 8.2.2 provides a full list of AEs of special interest for this compound.

Adverse events of special interest (AESIs) of anaphylaxis reactions, systemic reactions, and local injection site reactions are collected via targeted eCRF. Systemic reactions with preferred terms such as injection related reaction or administration related reaction will be considered non-allergic reactions; those with other preferred terms will be considered allergic/hypersensitivity reactions. The AESIs of opportunistic infections, malignancies, serious CVT events and serious ischemic events will be identified from a list of relevant preferred terms maintained within a project level reference dataset; created based on the latest version of the MedDRA dictionary available at the time of database freeze for this study (See Program Safety Analysis Plan for additional details).

ECG Parameters

RR Interval

All ECG parameters required in this study will be databased, and therefore, further derivations will not be performed by Stats and Programming. The definitions of these parameters are given in this section.

- If RR interval (msec) is not databased, then RR can be derived as :
 - [1] If QTcB is machine read & QTcF is not provided, then :

$$RR = \left[\left(\frac{QT}{QTcB} \right)^2 \right] * 1000$$

- [2] If QTcF is machine read and QTcB is not provided, then:

$$RR = \left[\left(\frac{QT}{QTcF} \right)^3 \right] * 1000$$

- If ECGs are manually read, the RR value should be a collected value and will not be derived.

Corrected QT Intervals

- When not databased, corrected QT intervals by Bazett's (QTcB) and Fredericia's (QTcF) formulas will be calculated, in msec, depending on the availability of other measurements.
- If RR interval (msec) is provided then missing QTcB and/or QTcF will be derived as :

ECG Parameters

$$QTcB = \frac{QT}{\sqrt{\frac{RR}{1000}}}$$

$$QTcF = \frac{QT}{3\sqrt{\frac{RR}{1000}}}$$

- Individual maximum QTc(F) and QTc(B) values will also be summarised by treatment group for each scheduled study visit to show the number of subjects with maximum values (msec) in the following categories:
 - ≤ 450
 - 450 < to ≤ 480
 - 480 < to ≤ 500
 - > 500
- Additionally, individual maximum changes from baseline in QTc(F) and QTc(B) values will be summarised by treatment group for each scheduled study visit to show the number of subjects with maximum changes (msec) in the following categories:
 - < -60
 - ≥ -60 to < -30
 - ≥ -30 to < 0
 - ≥ 0 to < 30
 - ≥ 30 to < 60
 - ≥ 60

Laboratory Parameters

- If a laboratory value which is expected to have a numeric value for summary purposes, has a non-detectable level reported in the database (values below the lower limit of quantification), where the numeric value is missing, but typically a character value starting with '<x' or '>x' (or indicated as less than x or greater than x in the comment field) is present, the lower limit of quantification for that particular parameter will be used to impute the corresponding numeric value as half the lower limit of quantification for that measure (LLQ/2).
- The above imputation of half the lower limit of quantification for that measure (LLQ/2) will also be applied to all biomarker parameters.
- Regarding blood eosinophil laboratory data please reference Section [10.6.3](#).

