
 • Summary Statistics will be represented by study visit • The mean change at Week 32 will presented with the corresponding 95% CI and p-value in the table • The mean change at Week 32 will presented with the corresponding 95% CI in the figure
--

On-treatment Phase

 • An On-Treatment “de jure” analysis will also be performed which does not consider any data collected following treatment discontinuation (see On-Treatment definition within Section 10.4)
--

Other Statistical Analyses

Other Endpoint

 • Change from baseline in inflammatory biomarkers expression at week 32. The following biomarker parameters will be reported: CCL13, CCL17, ECP, EDN, Eotaxin1, Total IL-5, IL-13, MDC, Periostin, TSLP

Model Results Presentation

 • A log-transformation will be applied to each biomarker parameter prior to analysis. • Summary Statistics will be represented by study visit, including ratio to baseline • See Section 10.6.4 for further information regarding biomarker results below the lower limit of quantification

On-treatment Phase

 • An On-Treatment “de jure” analysis will also be performed which does not consider any data collected following treatment discontinuation (see On-Treatment definition within Section 10.4).

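### SAP 10.6.4 is scoped to results below the quantification limit but also lists `>x` results as triggers, with LLQ/2 as the only replacement value

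*SAP*

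**What the plan says.** The rule is under Laboratory Parameters in SAP 10.6.4. It concerns a laboratory value that should be numeric but "has a non-detectable level reported in the database (values below the lower limit of quantification"). It then describes how such a value appears in the data: the number is missing, "but typically a character value starting with '<x' or '>x". The comment field counts as well: "or indicated as less than x or greater than x in the comment field) is present, the lower limit of quantification" is then the basis for the substitute. One replacement is given, which is to "impute the corresponding numeric value as half the lower limit of quantification for that measure (LLQ/2").

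The next bullet extends the rule: "The above imputation of half the lower limit of quantification for that measure (LLQ/2) will also be applied to all biomarker parameters". The bullet after that exempts one analyte: "Regarding blood eosinophil laboratory data please reference Section" 10.6.3.

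SAP 8.1.2 names ten biomarkers (CCL13, CCL17, ECP, EDN, Eotaxin1, Total IL-5, IL-13, MDC, Periostin, TSLP). For these, "A log-transformation will be applied to each biomarker parameter prior to analysis", and they are summarised by visit with ratio to baseline. Its pointer back to 10.6.4 mentions only results under the LLQ. SAP 10.7.2 likewise refers only to below-limit results. Neither document has a rule for results above an upper limit of quantification (ULQ).

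**The concern.** LLQ/2 is a common convention for a `<x` result. Applied to a `>x` result, it moves a value from above the top of the assay range to below the bottom. `>x` is listed twice, once as a character flag and once in words for the comment field, so a programmer could reasonably code it as a trigger.

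Biomarkers are summarised on the log scale, where one misplaced extreme carries a lot of weight. The study has a single arm compared with its own baseline, so no control group would expose an artefact of this kind. The rule also covers safety laboratory values, where a very high result could enter the chemistry and haematology change-from-baseline summaries (Tables 3.44 to 3.47) as a very low one.

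**Working it through.** The plan gives no figure to reproduce. The check is a comparison of texts, followed by an illustration on assumed inputs.

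**Step 1: the two readings of the sentence.**

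| Element of SAP 10.6.4 | Covers `<x` | Covers `>x` |
|---|---|---|
| Stated scope (below the LLQ) | yes | no |
| Character-value trigger | yes | yes |
| Comment-field trigger | yes | yes |
| Replacement given | LLQ/2 | LLQ/2 (no other value offered) |

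- Follow the triggers: a `>x` result becomes LLQ/2.
- Follow the scope: a `>x` result has no rule. SAP 10.7.2 adds no imputation for it, so with no numeric value it would drop out of numeric summaries.

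**Step 2: what the trigger reading does to one subject.** Assume LLQ = 1 and ULQ = 100, so LLQ/2 = 0.5.

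| Baseline | Week 32 | True ratio | Ratio as programmed |
|---|---|---|---|
| 50 | `>100` | above 2 | 0.5/50 = 0.01 |
| `>100` | 50 | below 0.5 | 50/0.5 = 100 |
| `>100` | `>100` | unknown | 0.5/0.5 = 1 |

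The first row is a false fall and the second a false rise. The third shows no change.

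**Step 3: what it does to the geometric mean ratio.** Let R = ULQ/LLQ. Each `>x` result is understated by at least ULQ/(LLQ/2) = 2R. Compared with setting such results to ULQ, the geometric mean ratio is multiplied by

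exp(−(p_week32 − p_baseline) × ln(2R)),

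where the two p are the shares of `>x` results at each visit. With p_baseline = 0:

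| Assumed R | ln(2R) | p_week32 = 1% | 5% | 10% |
|---|---|---|---|---|
| 20 | 3.689 | 0.964 | 0.832 | 0.692 |
| 100 | 5.298 | 0.948 | 0.767 | 0.589 |
| 1000 | 7.601 | 0.927 | 0.684 | 0.468 |

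For example, exp(−0.05 × 5.298) = exp(−0.265) = 0.767. If the 5% occurs at baseline only, the factor is 1/0.767 = 1.30. If the shares are equal, it is 1.00 whatever the assay range.

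**The case against.** The strongest reply is that this is a below-LLQ rule with a slip in its wording. A result above the assay range is neither non-detectable nor below the LLQ, so it does not meet the opening condition. The cross-references in SAP 8.1.2 and 10.7.2 speak only of below-limit results, which also points to a drafting error. This stands. A reader might infer that the SAP directs the highest results to be turned into the lowest. The text does not support that, because the sentence conflicts with itself and its stated scope says otherwise.

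A reader might also infer that the biomarker effect is reversed for every affected subject. That does not follow either: it requires `>x` at one visit only, and the ratio is 1 when both visits are `>x`.

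The reach is small. Biomarker change is an exploratory endpoint (SAP 2.2), reported in summary Tables 2.37 to 2.46 with no model or test planned. Safety laboratory data are summarised descriptively.

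The objection does not remove the need for a correction. Even on the intended reading, above-range results have no rule, and the highest values would be lost from the numeric summaries.

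**Conclusion.** The point holds as an internal contradiction in an operative data-handling rule. Programmed by its triggers, the rule gives above-range results the lowest value used; read by its scope, it leaves them without a value.

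The size is unknown. The factor of 0.77 rests on R = 100, 5% of Week 32 values above range and none at baseline. Neither document states an assay range or how often `>x` results are expected, so it should not be read as a predicted 23% false reduction (1 − 0.767 = 0.233). If no `>x` results occur, or they occur equally often at both visits, there is no bias in the geometric mean ratio from this source.

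The consequences stop at the exploratory biomarker summaries and the descriptive safety laboratory summaries. Blood eosinophils, the secondary pharmacodynamic endpoint, are handled in 10.6.3. The primary endpoint and the other secondary endpoints are not touched. The correction is cheap and worth making before database freeze.

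**What to change.** In SAP 10.6.4, delete `>x` and the matching comment-field wording from the LLQ/2 rule, so that it applies to `<x` results only. Add a sentence for above-range results in laboratory and biomarker data, for example: set to the reported upper limit x and flag in the listing. Other conventions, such as treating the value as right-censored, would also serve; what matters is that one is stated.

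Reporting the number of below-LLQ and above-ULQ values per visit beside each biomarker summary would help readers but is optional.

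The cost is one or two sentences in the SAP and a small programming change. No new data are needed.

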10.7. Appendix 7: Premature Withdrawals & Handling of Missing Data

10.7.1. Premature Withdrawals

Element	Reporting Detail
General	
 A subject will be considered to have completed study treatment if he/she receives study treatment at Visit 9 (Week 28) and completes the Visit 10/Exit Visit (Week 32). A subject will be considered to have completed the study if they continue to participate in the study until the Exit Visit assessments have been completed (regardless of whether the subject completed the study treatment schedule). Subjects who discontinue study treatment or withdraw early will not be replaced in the study. The number of subjects who discontinue study treatment or withdraw early will be summarised and listed. All available data from subjects who were withdrawn from the study will be listed and all available data up to and including the date of early withdrawal will be included in summary tables and figures, unless otherwise specified.
Pre-Screen Failures, Screen Failures and Run-in Failures	
For the purposes of this study pre-screen failures, screen failures and run-in failures will be defined as follows:
 
 Subjects will be assigned a study number at the time of signing the informed consent (Pre-screen Visit). Subjects who do not progress to the Screening Visit will be deemed a pre-screen failure. Those subjects that complete at least one additional Visit 1 (Screening) procedure but do not enter the run-in period will be designated as screen failures. Those subjects that enter the run-in but do not subsequently receive study treatment will be designated as run-in failures.

10.7.2. Handling of Missing Data

Element	Reporting Detail
General	
 Missing data occurs when any requested data is not provided, leading to blank fields on the collection instrument : 
 These data will be indicated by the use of a “blank” in subject listing displays. Unless all data for a specific visit are missing in which case the data is excluded from the listing. Answers such as “Not applicable” and “Not evaluable” are not considered to be missing data and should be displayed as missing. Results which are found to be below the limit of quantification (BLQ) are not missing data and will be included in all displays. See Section 10.6 for the handling of this data. The ACQ-5 score will be considered as missing if <4 items of the questionnaire

Element	Reporting Detail
	
are completed at a visit. ACQ-5 Responder/Non-responder category will be missing if the overall ACQ-5 score is missing.
 
 • If a blood eosinophil count of zero is reported, it will be imputed with half of the lowest possible blood eosinophil count, where applicable, prior to log transforming the data (Note: this imputation has typically been $0.5 * 0.01 \text{ GI/L} = 0.005 \text{ GI/L}$ for previous mepolizumab studies). • Missing values will not be imputed for any of the other endpoints.
Outliers	
 • Any subjects excluded from the summaries and/or statistical analyses will be documented along with the reason for exclusion in the clinical study report.

10.7.2.1. Handling of Missing or Partial Dates

Element	Reporting Detail
General	
 • The eCRF allows for the possibility of missing or partial dates (i.e., only month and year is captured) to be recorded for event start and end dates. • The recorded missing or partial date will be displayed in listings as captured.
Concomitant Medications	
 • Partial dates for any concomitant medications recorded in the CRF will be imputed using the following convention: 
 ◦ If the partial date is a start date, a '01' will be used for the day and 'Jan' will be used for the month ◦ If the partial date is a stop date, a '28/29/30/31' will be used for the day (dependent on the month and year) and 'Dec' will be used for the month.
Adverse Events, Exacerbations	
 • Any partial dates for adverse events and exacerbations will be raised to data management. If the full date cannot be ascertained, the following assumptions will be made: 
 ◦ If the partial date is a start date, a '01' will be used for the day and 'Jan' will be used for the month. ◦ However, if these result in a date prior to the start of treatment and the event could possibly have occurred during treatment from the partial information, then the study treatment start date will be assumed to be the start date and hence the event is considered On-treatment (worst case), as per Appendix 4: Treatment Phases. ◦ If the partial date is a stop date, a '28/29/30/31' will be used for the day (dependent on the month and year) and 'Dec' will be used for the month. • The above listed imputations will also be applied when calculating the time to onset and the duration of the event containing missing or partial start and end dates. • Start or end dates which are completely missing (i.e. no year specified) will remain missing, with no imputation applied. Consequently, time to onset and duration of such events will be missing.

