07	Inclusion criteria # 8 – Not receiving Omalizumab treatment based on weight and IgE levels, for at least the 4 months prior to Visit 1.
08	Inclusion criteria # 9 – No history of two or more exacerbations requiring treatment with systemic corticosteroids (intramuscular, intravenous, or oral) in the 12 months prior to Visit 1 despite the use of high-dose ICS. [Note: For subjects receiving omalizumab for ≥ 8 months, at least one exacerbation must have occurred while on omalizumab treatment. For subjects receiving maintenance oral corticosteroids, the corticosteroid treatment for the exacerbations must have been a two-fold dose increase or greater.]
09	Continuation to treatment criteria # 1 – Asthma symptoms not uncontrolled at Visit 2, as

Number	Exclusion Description
	defined by an ACQ-5 score of <1.5.
10	Continuation to treatment criteria # 2 – Subjects who experience an asthma exacerbation during run-in who have not returned to their baseline asthma status within one week of Visit 2.
11	Continuation to treatment criteria # 3 – Any subject with changes in the dose or regimen of ICS, and/or additional controller medication (except for treatment of an exacerbation) during the run-in period.
12	Continuation to treatment criteria # 4 – Subjects who do not receive their last dose of Omalizumab during the correct period, as defined by: 
 For subjects receiving omalizumab every 4 weeks, their last dose is received <3 or >5 weeks prior to Visit 2. For subjects receiving omalizumab every 2 weeks, their last dose is received <1 or >3 weeks prior to Visit 2.
13	Any subject with changes in the dose or regimen of baseline ICS, and/or additional controller medication during open-label treatment. N.B. This excludes the use of OCS for the treatment of an asthma exacerbation.
14	Use of any prohibited medication during the study [1].
15	Receiving the incorrect study treatment at any point during the study.

NOTES:

- [1] See Protocol Section 6.8.2 for the list of prohibited medications within this study.

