- ¹For all subjects, i.v. or oral steroid (e.g., prednisone) for at least 3 days or a single IM CS dose is required. For subjects on maintenance systemic corticosteroids, at least double the existing maintenance dose for at least 3 days is required.
- Within each subject, exacerbations that occurred less than seven days apart will be collapsed into a single exacerbation. Exacerbations for which the collapsing has already been performed will be included in the summaries and analyses. Exacerbations will be displayed in listings as captured within the eCRF. Exacerbations which are collapsed into a single exacerbation will be highlighted.
- The collapsed exacerbation records will be constructed as follows:
 - Start date (ASTDT) is the start date of the first exacerbation in the series
 - End date (AENDT) is the end date of the last exacerbation in the series
 - Outcome (CEOUT) is the worst outcome in the series (worst to best is Fatal, Not Resolved, Resolved)
 - Cause (EBCAUSE) is the cause associated with the first exacerbation in the series
 - Withdrawal due to exacerbation (EBWD), OCS taken for exacerbation (OCSEXB), corticosteroids taken for exacerbation (CTSEXB), hospitalization due to exacerbation (HSPEXB), emergency visit due to exacerbation (EREXB), and intubation for exacerbation (INTUBEXB) are set to 'Y' if any value for the respective variable in the series equals 'Y'
 - Number of telephone calls (TPCNUM), home day visits (HMDYVSN), home night visits (HMNTVSN), home day+night visits (HMDYNTV), office visits (OFCVSN), urgent care/outpatient visits (UCOUTVSN), emergency room visits (ERVSN), days in intensive care (ICSDYNUM), days in general ward (GWDYNUM) and days hospitalized (HSPDYNUM) are the sum of all of the values in the series for each respective variable

Blood Eosinophils

- Blood eosinophils will be log-transformed prior to analysis. Summary statistics will include geometric mean, and a measure of spread (SD or SE) on the natural log scale.

- If a blood eosinophil count of zero is reported, it will be imputed with half of the lowest possible blood eosinophil count, where applicable, prior to log transforming the data (Note: this imputation has typically been $0.5 * 0.01 \text{ GI/L} = 0.005 \text{ GI/L}$ for previous mepolizumab studies).

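### As worded, SAP 10.7.2.1 replaces a recorded month with January or December, because the imputation is not limited to dates whose month is missing

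*SAP*

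**What the plan says.** SAP 10.7.2.1 introduces partial dates with "The eCRF allows for the possibility of missing or partial dates (i.e., only month and year is captured". The same rule is then given twice, once for concomitant medicines and once for adverse events and exacerbations:

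- Start: "If the partial date is a start date, a '01' will be used for the day and 'Jan' will be used for the month".
- Stop, day: "If the partial date is a stop date, a '28/29/30/31' will be used for the day (dependent on the month and year".
- Stop, month: "Dec' will be used for the month".
- No year at all: "Start or end dates which are completely missing (i.e. no year specified) will remain missing". By implication, a date with only a year is also partial.

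Adverse events and exacerbations have two protections. First, "Any partial dates for adverse events and exacerbations will be raised to data management", and imputation follows only if the full date cannot be found. Second, an imputed start that falls before treatment is moved up to first dose when the event may have been on treatment. The section applies the imputed dates to time to onset and duration. Listings show the date as recorded.

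Medicines have neither protection in 10.7.2.1. SAP 10.4.4 does, however, treat a partly dated medicine as on treatment unless something shows otherwise.

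**The concern.** The only kind of partial date the section describes is one whose month is known, yet the rule supplies a month. A programmer who follows the text would overwrite recorded information. One who infers the intent would keep it. The two would produce dates that are months apart within a 32-week study.

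The outputs directly exposed are onset time and duration, including the time-to-onset entry in each special-interest event profile (SAP 8.2.2). Time to first exacerbation (Table 2.19, Figure 2.8), the exacerbation count after collapsing (SAP 10.6.3) and the table of asthma medicines started before treatment (Table 1.21) may also be affected.

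**Working it through.** The SAP gives no figure on this point, so there is none to reproduce. The check compares the rule as written with a version that keeps the recorded month.

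**1. The texts side by side.** The start and stop rules carry no condition about a missing month. Three other places assume the month is used:
- The stop day depends on the month, which is pointless if the month is always December.
- SAP 10.4.3 compares the recorded month and year of an event's onset with first dose.
- SAP 10.4.4 does the same for a medicine's stop date.

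So the rule conflicts with its own section and with two others.

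**2. Worked dates.** Assume first dose on 15 Mar 2017. Week 32 is then 15 Mar + 224 days = 25 Oct 2017. SAP 10.4.3.1 gives onset day = onset − first dose + 1 and duration = resolution − onset + 1.

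| Recorded | As written | Month kept |
|---|---|---|
| Adverse event start, Aug 2017 | 1 Jan, moved up to 15 Mar: onset day 1 | 1 Aug: onset day 139 + 1 = 140 |
| Same event, stop also Aug 2017 | 31 Dec: duration 291 + 1 = 292 days | 31 Aug: duration 30 + 1 = 31 days |
| Exacerbation stop, Apr 2017 | 31 Dec, 67 days after Week 32 | 30 Apr |
| Controller start, Jun 2017 | 1 Jan, before treatment | 1 Jun, on treatment |

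The move to first dose does not always apply. With first dose on 3 Oct 2016, an event recorded as May 2017 becomes 1 Jan 2017, which is on treatment but 120 days before 1 May.

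**3. Size of the start shift, given that a start date is partial.** All 365 first-dose days in a year were crossed with all 224 study days, each equally weighted (an assumption).
- Adverse events and exacerbations: mean backward shift about 89 days, maximum 224.
- Medicines: mean 182 days, maximum 364. About 69% of on-study starts are dated before first dose. Keeping the month reduces this to about 6%, namely starts in the month of first dose.

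**4. Collapsing, only if imputed dates feed it.** SAP 10.6.3 says: "Within each subject, exacerbations that occurred less than seven days apart will be collapsed into a single exacerbation". Suppose exacerbation A truly ends on 12 Apr and B starts on 7 Aug 2017, a gap of 117 days.
- A's stop recorded as Apr 2017: as written it becomes 31 Dec, the gap is −146 days, and the two merge. With the month kept, the gap is 99 days.
- B's start recorded as Aug 2017: as written it becomes 15 Mar, the gap is −28 days, and the two merge. With the month kept, the gap is 111 days.

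In 200,000 simulated pairs of separate exacerbations (uniform timing, 10-day episodes, one relevant date partial), about 82% merge under the rule as written and about 14% with the month kept. The timing and episode length are assumptions, not figures from the documents.

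**The case against.** The strongest reply is that this is a drafting gap. The stop-day wording, the test of whether the partial information allows an on-treatment event, and the month-and-year comparisons in SAP 10.4.3 and 10.4.4 all suggest that January and December were meant to fill a missing month. Programmers may already work that way. That is plausible, but it shows that the section contradicts itself. It does not remove the operative wording.

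The safeguards are also real. Exacerbations are reviewed at every visit, subjects carry a worksheet (Protocol 7.4.8), and partial event dates are queried before imputation. Few may remain.

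A reader might infer more than the documents support:

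- **Per Protocol membership.** Exclusion 13 removes "Any subject with changes in the dose or regimen of baseline ICS, and/or additional controller medication during open-label treatment", so a back-dated change might seem to keep a subject in. SAP 4.1 has deviations tracked by the study team, reviewed before freeze and held in their own dataset. Nothing says they are derived from imputed dates.
- **Medicines left wholly uncorrected.** SAP 10.4.4 still counts a partly dated medicine as taken during treatment, and no listed table uses the subset started during treatment. Table 1.21 is the exposed display.
- **Shifts of up to 11 months for on-study event starts.** The move to first dose limits these to about 224 days.
- **Collapse to one exacerbation whatever the true number.** That needs both dates of one record to be partial, every other episode in the same calendar year, and imputed dates driving the collapse. A course that crosses New Year can defeat it.

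**Conclusion.** The point holds as a defect of wording with definite consequences if it is followed literally. Adverse-event and exacerbation dates still partial after query would get wrong onset times and durations. Starts move back by up to about 224 days, and stops move to 31 December with no cap at study exit.

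Two further effects are conditional, because the SAP does not say whether imputed dates feed these steps. Time to first exacerbation would be shortened, which works against mepolizumab. Merging would lower the on-study exacerbation count, which favours mepolizumab in the comparison with the 12-month history taken at screening. The net direction is therefore mixed.

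For medicines, the consequence is a misplaced entry in a descriptive table. The number of partial dates is not given, so the effect on any reported result cannot be sized; the percentages above apply only to records with a partial date. The ACQ-5 ITT primary analysis is visit-based and is not affected.

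**What to change.** Amend SAP 10.7.2.1 before database freeze, for both medicines and events:

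1. When month and year are recorded, impute the first day of that month for a start and its last day for a stop.
2. Use January or December only when the month is missing.
3. Cap imputed adverse-event and exacerbation stop dates at the Exit or last-contact date.

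It would also help to state whether imputed dates are used for time to first exacerbation and for the collapsing step. The 7-day rule itself should stay as it is, since Protocol 7.3.2.4 sets it. The existing move of event starts to first dose can also stay; it still serves events recorded in the month of first dose.

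The cost is a few lines of text and a small programming change, with no new data.
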